### 3 Investigational plan

#### 3.1 Study design

This is a Phase Ib, open-label, dose-finding study of the JAK inhibitor INC424 tablets administered orally to patients with Primary Myelofibrosis (PMF), Post-Polycythemia Vera-Myelofibrosis (PPV-MF) or Post-Essential Thrombocythemia-Myelofibrosis (PET-MF) and baseline platelet counts  $\geq 50 \times 10^9/L$  and  $<100 \times 10^9/L$ .

The study will consist of 2 periods:

- The core study period [first 168 days of study]
- The extension study period [beyond Week 24 (168 days) to 3 years].

The core study includes patients in one of two phases (Figure 3-1), (a) a dose escalation phase and (b) a safety expansion phase.

In the dose escalation phase, successive cohorts of newly enrolled patients will receive increasing doses of INC424 until the MSSD is determined. The MSSD will be the dose level most closely associated with a posterior DLT probability of between 16% and 33% that does not also have a greater than 25% probability of excessive toxicity. In the safety expansion phase, 20 patients in total (10 patients from each stratum), additional to those treated at the MSSD during dose escalation, will be treated at the respective MSSD for their stratum.

The treatment period for an individual patient is 3 years [except in the UK, which is up to LPFV + 156 weeks]: it will begin on Study Day 1 and will continue until the patient completes the study or is permanently discontinued.

The approximate number of patients planned to be enrolled in the Dose-Determining Set (DDS) for this study is 72, assuming 3 patients are treated at each dose level and 5 dose levels are tested in both strata, and including the additional patients to be enrolled into the 10 mg BID dose which is to be evaluated as a starting dose.

DLT will be defined as the occurrence of any of the following **treatment-related** toxicities occurring through Study Day 28:

- any grade  $\geq 2$  hemorrhagic event
- any grade thrombocytopenia requiring PLT transfusion
- PLT counts  $< 25 \times 10^9/L^*$
- grade 4 neutropenia (ANC  $< 0.5 \times 10^9/L$ )\*

- grade  $\geq$  3 febrile neutropenia\*
- grade  $\geq$  2 total serum bilirubin with coincident direct bilirubin  $\geq$  0.5 mg/dL
- grade 3 non-hematologic toxicity for  $\geq$  7 consecutive days
- grade 4 non-hematologic toxicity

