**\* At the discretion of the Investigator, laboratory values can be confirmed with a second assessment. In this case, only the result of the second assessment will be considered valid and final.**

Adverse events occurring after Study Day 28 will not be considered DLTs, however, they may be considered in further decisions regarding the number of patients to enroll in a given dosing cohort. If a patient is not followed for the 28-day period following Study Day 1 due to discontinuation, for reasons other than DLTs, or if, from Study Day 1 through Study Day 28, a patient misses  $> 6$  consecutive doses of treatment or  $> 20\%$  of the planned study drug doses, another patient will be enrolled into that dose level and stratum. For toxicities which, by definition, require a time-window for them to be defined as DLTs (grade 3 non-hematologic toxicity for  $\geq$  7 consecutive days) a subsequent visit(s) and/or laboratory assessment(s) must be scheduled accordingly, in order for this toxicity to qualify as a DLT. A minimum of 9 evaluable patients from each stratum (stratum 1 consists of patients with baseline PLT counts  $75-99 \times 10^9/L$  and stratum 2 consists of patients with baseline PLT counts  $50-74 \times 10^9/L$ ) must be treated at the dose declared to be the MSSD.

Enrollment of patients and dose escalation will be performed as described in [Section 5.1.2.1](#), [Section 5.1.2.2](#), [Section 5.1.2.3](#) and [Section 5.1.2.4](#).

Intra-patient escalation during the dose escalation phase of the study will be allowed according to the rules described in the [Section 5.1.2.6](#).

[figure not shown]
Following determination of the MSSD, a safety expansion phase will be conducted. Patients from both strata can be enrolled simultaneously during the safety expansion phase, allocated to a dose equal to the respective MSSD for their stratum. If the MSSD is the same in both strata, all patients in the safety expansion phase will be treated with the same dose, regardless of the baseline PLT counts.

In the safety expansion phase, the safety and tolerability of the MSSD will be further evaluated with the purpose of establishing that this dose is suitable for use in the low-platelet population of patients with MF. The Bayesian logistic regression model (BLRM) with escalation with overdose control (EWOC) will continue to be updated with data from patients participating in the safety expansion phase.

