### 5.1.2.8 Dose-limiting toxicity (DLT)

Dose-limiting toxicity (DLT) will be defined as the occurrence of any of the **treatment-related** toxicities occurring up to and including Study Day 28, which are listed in [Table 5-3](#), using the Common Terminology Criteria for Adverse Events (CTCAE) v4.03.

For the purpose of dose-escalation decisions, only DLTs will be necessarily considered and included in the BLRM. However, adverse events, which occur after Study Day 28 and meet all the criteria for the DLT definition apart from the timing of occurrence, will be considered in ultimate decisions of dose escalation and determinations of how many patients should be evaluated at a given dose level. Prior to enrolling patients into a higher dose level, all adverse events will be reviewed for all patients at the current and the previous dose levels.

For toxicities which, by definition, require a time-window for them to be defined as DLTs (grade 3 non-hematologic toxicity for  $\geq 7$  consecutive days), a subsequent visit(s) and/or laboratory assessment(s) must be scheduled accordingly, in order for this toxicity to qualify as a DLT. For example, if a grade 3 non-hematologic toxicity is observed, it must be also observed at least 7 days later, with no intervening lower grades, in order to qualify as a DLT.

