**Table 5-3 Criteria for defining dose-limiting toxicities**

Toxicity	Any of the following treatment-related criteria (occurring through Study Day 28)
Hematology	PLT counts $< 25 \times 10^9/L$ * grade 4 neutropenia ( $ANC < 0.5 \times 10^9/L$ )* grade $\geq 3$ febrile neutropenia*
Other AEs	any grade thrombocytopenia requiring PLT transfusion any grade $\geq 2$ hemorrhagic event grade $\geq 2$ serum bilirubin with coincident direct bilirubin $\geq 0.5$ mg/dL grade 3 non-hematologic toxicity for $\geq 7$ consecutive days grade 4 non-hematologic toxicity

\* At the discretion of the Investigator, laboratory values can be confirmed with a second assessment. In this case, only the result of the second assessment will be considered valid and final.

Patients who experience a DLT will have their therapy with INC424 interrupted and will be followed as described in the [Table 5-4](#). After recovery from the toxicity in question, if the Investigator believes that it is in the patient's best interest to resume therapy with INC424, the patient may resume therapy, only after consultation with the Sponsors, according to the guidelines described in the [Section 5.1.3](#) and the [Table 5-4](#).

However, the patient must be permanently discontinued from study medication and withdrawn from the study, if **any** of the following DLTs occur:

- any grade  $\geq 3$  hemorrhagic event
- 2nd episode of grade  $\geq 3$  febrile neutropenia
- grade 3 renal toxicity for  $\geq 7$  consecutive days
- grade 4 renal toxicity

- grade 4 serum bilirubin with direct bilirubin  $\geq 0.5$  mg/dL
- grade 4 non-hematologic toxicity

If, from Study Day 1 through Study Day 28, a patient misses  $> 6$  consecutive doses of treatment or  $> 20\%$  of the planned study drug doses, the patient will not be evaluable for DLTs. The patient can continue in the study, but another patient has to be enrolled at the same dose level and stratum in order to reach the required number of patients in the cohort.

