## 7 Safety monitoring and reporting

## 7.1 Adverse events

### 7.1.1 Definitions and reporting

An Adverse Event for the purposes of this protocol is defined as the appearance of (or worsening of any pre-existing) undesirable sign(s), symptom(s), or medical condition(s) that occur after patient's signed informed consent has been obtained. Abnormal laboratory values or test results occurring after informed consent constitute Adverse Events only if they induce clinical signs or symptoms, are considered clinically significant, require therapy (e.g., hematologic abnormality that requires transfusion), or require changes in study medication(s).

Adverse Events that begin or worsen after informed consent should be recorded in the Adverse Events eCRF. Conditions that were already present at the time of informed consent should be recorded in the Medical History eCRF. Adverse Event monitoring should be continued for at least 30 days following the last dose of study treatment. Adverse Events (including lab abnormalities that constitute AEs) should be described using a diagnosis whenever possible, rather than individual underlying signs and symptoms. When a clear diagnosis cannot be identified, each sign or symptom should be reported as a separate Adverse Event.

Adverse Events will be assessed according to the Common Terminology Criteria for Adverse Events (CTCAE) version 4.03. If CTCAE grading does not exist for an Adverse Event, the severity of mild, moderate, severe, and life-threatening, **or** grades 1-4, will be used. CTCAE grade 5 (death) will not be used in this study; rather, information about deaths will be collected through a Death form. The occurrence of Adverse Events should be sought by non-directive questioning of the patient during the screening process after signing informed consent and at each visit during the study. Adverse Events also may be detected when they are volunteered by the patient during the screening process or between visits, or through physical examination, laboratory test, or other assessments. As far as possible, each Adverse Event should be evaluated to determine:

- The severity grade (CTCAE grade 1-4)

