- Causality to the Adverse Event (reasonable possibility that the AE is related to the study drug). Since this is an open-label study, the relationship to study drug is only assessed for INC424. For study investigative sites in EU: if the AE is serious, then the causality to INC424 needs to be assessed to comply with requirements according to the EU Clinical Studies Directive.
- Start and end dates, unless unresolved at the follow-up visit
- Action taken with respect to study drug (none, dose adjusted, temporarily interrupted, permanently discontinued, unknown, not applicable)
- Outcome (not recovered/not resolved, recovered/resolved, recovering/resolving, recovered/resolved with sequelae, fatal, unknown)
- Whether it is serious, as per SAE definition provided in [Section 7.2](#).

**Unlike routine safety assessments, SAEs are monitored continuously and have special reporting requirements, see [Section 7.2](#).**

All Adverse Events should be treated appropriately. Treatment may include one or more of the following: no action taken (i.e. further observation only); study drug dosage adjusted/temporarily interrupted; study drug permanently discontinued due to this adverse event; concomitant medication given; non-drug therapy given; patient hospitalized/patient's hospitalization prolonged. The action taken to treat the adverse event should be recorded on the Adverse Event eCRF.

Once an Adverse Event is detected, it should be followed until its resolution or until it is judged to be permanent, and assessment should be made at each visit (or more frequently, if necessary) of any changes in severity, the suspected relationship to the study drug, the interventions required to treat it, and the outcome.

Disease progression should not be regarded or reported as an Adverse Event itself unless associated with a separate Adverse Event.

Whenever possible, a diagnosis should be reported instead of underlying signs and symptoms.

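### A treatment-related death through Study Day 28 that meets no listed DLT criterion is missing from the primary DLT rate, the Dose-Determining Set and the BLRM

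*Protocol*

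**What the plan says.** **DLT list.** Protocol 3.1 opens its list of eight treatment-related criteria with "DLT will be defined as the occurrence of any of the following", and Table 5-3 repeats them. Death is not among them. Several criteria apply below grade 4: hemorrhage from grade 2, platelets under 25 x 10^9/L, "any grade thrombocytopenia requiring PLT transfusion", febrile neutropenia from grade 3, and grade 2 or higher bilirubin with direct bilirubin at or above 0.5 mg/dL. For other non-hematologic events the routes are "grade 4 non-hematologic toxicity" or grade 3 for at least 7 days. Section 5.1.2.8 adds that for the grade 3 route "it must be also observed at least 7 days later, with no intervening lower grades".

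**Grading.** Section 7.1.1 states: "CTCAE grade 5 (death) will not be used in this study; rather, information about deaths will be collected through a Death form". Severity runs from 1 to 4. Fatality appears only as an outcome code ("recovered/resolved with sequelae, fatal, unknown"), and no section links that code to a grade or to a DLT.

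**Analysis set.** Protocol 9.1.3 admits a patient to the DDS either through adequate exposure with complete safety evaluations to Day 28, or through discontinuation due to DLT. SAP 2.1.1 widens the second route to any patient with a DLT. Neither has a route for death without a DLT.

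**Replacement.** Section 3.1 begins its rule with "If a patient is not followed for the 28-day period following Study Day 1 due to discontinuation, for reasons other than DLTs" and makes a further enrolment mandatory. Section 9.4.3 makes it optional. Section 6.1.4.1 says withdrawn patients are not replaced, with an exception only for missed doses.

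**The concern.** The primary endpoint is the DLT incidence rate, and section 5.1.2.8 commits only DLTs to the BLRM. If a related death meets no listed criterion, the most severe possible outcome leaves both the numerator and the denominator. The omission has one direction: it can only lower the observed DLT count. Whether a related death counts would also turn on the grade the site happened to enter, because the protocol gives no grading rule for fatal events.

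SAP 2.1.1 already repaired a neighbouring hole by bringing into the DDS patients who had a DLT but resumed treatment. That repair does not reach a fatal event that is not a DLT in the first place.

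**Working it through.** **Step 1. Which related deaths fall through.** Read literally, by type of event:

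| Related fatal event through Day 28 | DLT as written? |
|---|---|
| Hemorrhage, grade 2 or higher | Yes |
| Platelets < 25 x 10^9/L, or thrombocytopenia needing transfusion | Yes |
| Grade 4 neutropenia, or febrile neutropenia grade 3 or higher | Yes |
| Bilirubin item met | Yes |
| Non-hematologic, recorded as grade 4 | Yes |
| Non-hematologic grade 3, death under 7 days from onset | No: cannot be observed again 7 days later |
| Non-hematologic grade 1-2 outside the listed items | No |
| Anemia, any grade including 4 | No: hematologic, and not listed |

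Grade 4 is therefore not the dividing line in either direction. For the last three rows, a patient who dies before completing the Day 28 evaluations fails both routes into the DDS.

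**Step 2. Reproduce the plan's model.** Inputs, all from protocol 9.4.2:
- Prior for (log α, log β), Table 9-1: weight 0.9 on means (-1.010, -0.259), SDs (0.876, 0.918), correlation -0.103; weight 0.1 on means (-1.447, -0.385), SDs (1.095, 1.412), correlation -0.065.
- Reference dose 30 mg/day.
- Model: logit π(d) = log α + β log(d/30), plus γ for stratum 2. Only stratum 1 is used here.
- Likelihood for r DLTs in n patients: π^r (1-π)^(n-r).
- Rule: the dose with the highest P(16% ≤ π < 33%) among doses with P(π ≥ 33%) < 0.25, at most one level up. The one-level cap is stated for the Appendix 13 simulations.

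Drawing from this prior reproduces the interval probabilities of Table 9-1 within 0.004. For example, prior P(π ≥ 33%) at 15 mg/day in stratum 1 is 0.168 in the table and 0.168 recomputed. Table C is also reproduced: after 0/3 at 10 mg/day, go to 15; after 1/3, stay at 10; after 2/3, stop.

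**Step 3. Effect of one uncounted death, first stratum 1 cohort at 10 mg/day.** The other two patients have no DLT. If the death is not counted and a third evaluable patient without DLT is added, the data are 0/3. If it is counted, they are 1/3.

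| Data | P(π ≥ 33%) at 10 mg | at 15 mg | Recommendation |
|---|---|---|---|
| 0/3 (not counted) | 0.034 | 0.059 | 15 mg/day |
| 1/3 (counted) | 0.192 | 0.273 | stay at 10 mg/day |
| 2/3 (counted, plus one other DLT) | 0.482 | 0.586 | stop |

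If the death is one of two true DLTs, leaving it out turns 2/3 into 1/3, that is, stop into stay.

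**Step 4. How far this carries.** After 0/3 at 10 and 0/3 at 15 mg/day, both 0/3 and 1/3 at 20 mg/day lead to 25 mg/day; P(π ≥ 33%) at 25 mg is 0.036 versus 0.134. The early flip also depends on a cohort of three: if the death is counted and a fourth patient without DLT is enrolled anyway, 1/4 at 10 mg/day gives 0.212 at 15 mg, under 0.25, and the model moves up.

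**The case against.** **The gap is small, and other safeguards see the event.** This largely stands. Thrombocytopenia is the drug's established DLT, and platelet and bleeding events are caught well below grade 4. A fatal event is an SAE (7.2.1), and 7.2.2 requires a report within 24 hours with relationship to study drug recorded. Section 5.1.2.3 puts non-DLT adverse events before the escalation meeting, 9.4.2 treats the model output as one input to a clinical assessment, and SAP 2.3.2 tabulates deaths and the adverse events of patients who died. None of this puts the event into the DLT rate, the DDS or the posterior.

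**Sites would naturally grade a fatal event 4.** That is plausible with grade 5 withdrawn, and a related non-hematologic event so graded is a DLT. But no sentence says so, and it would not help for anemia.

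**Escalation was finished by Amendment 4.** True: the amendment rationale reports an MSSD for both strata, so a change now cannot alter those decisions. It still governs the reported DLT rate, the updates with expansion data (3.1) and the final posterior table (SAP 2.3.1).

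Three stronger readings are tempting and not supported:
- A reader might infer that every related death recorded below grade 4 is lost. Step 1 shows that many such events count.
- A reader might infer that a sudden death would exist only on the Death form. The SAE rules contradict this.
- A reader might infer that the patient is certainly replaced. Sections 3.1, 6.1.4.1 and 9.4.3 disagree, and for the expansion part 9.4.3 allows an extra patient only for someone outside the Safety Set, which a treated patient is not.

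**Conclusion.** The concern holds in a narrow form. Applied exactly as written, the plan leaves a treatment-related death through Day 28 out of the primary DLT rate, the DDS and the BLRM when the event meets no listed criterion. The clear cases are a grade 3 non-hematologic event fatal in under 7 days, and fatal anemia at any grade. Exclusion from the DDS does not depend on which replacement rule is followed.

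One such event in the first cohort can move the model from staying at 10 mg/day to escalating (0.273 versus 0.059 at 15 mg/day, limit 0.25). In the later cohort tested it changed nothing. These figures show the effect of one event, not its probability: the documents give no rate for such deaths, and it is probably low. They rest on the Table 9-1 prior, cohorts of three and the one-level cap. The event would be known to the sponsors and reported as a death; the defect lies in the primary endpoint count.

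**What to change.** - **Protocol 3.1 and Table 5-3:** for the primary analysis, count any treatment-related death through Study Day 28 as a DLT event, whatever grade was recorded. An explicit death item is needed; a convention that fatal means grade 4 would still miss anemia.
- **SAP 2.1.1:** state that such a patient is in the DDS as a DLT. If enrolment has closed, this statement alone settles the final analysis.
- **Protocol 3.1, 6.1.4.1 and 9.4.3:** reconcile the three replacement rules so that such a patient is not handled as non-evaluable.

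The cost is a few lines of text and no new data, since relatedness and fatal outcome are already collected. The downside is that the DLT rate can only stay the same or rise.

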### **3.1.1      Investigational treatment, other study treatment, study treatment, supportive treatment**

During the study all patients will receive INC424 tablets (see [Section 5.1.1](#)). INC424 tablets will be the only investigational drug in this study ([Table 3-1](#)).

**Table 3-1      Study drugs**

Study drugs	
Investigational drug	INC424 tablets (5 mg)

### **3.1.2      Treatment arms**

All patients will receive INC424 tablets. See [Figure 3-1](#) for details regarding dose escalation.

### **3.1.3      Treatment duration**

The study will consist of 2 periods: the initial 24 weeks core treatment period from Study Day 1 to Study Day 168 and the extension treatment period from Study Day 168 (Week 24) until 3 years (Week 156). The core study period consists of a dose escalation phase and a safety expansion phase ([Figure 3-1](#)).

[For patients in the United Kingdom only:

After 3 years of study treatment, if the patient continues to benefit in the opinion of the Investigator and does not have access to study drug outside of this clinical trial, the patient may continue on study treatment until LPFV plus 3 years. After LPFV plus 3 years, if the study treatment is not commercially available and reimbursable in the UK, an alternative UK-specific free of charge (FOC) program exists to provide continued access for patients benefitting from the study treatment]

### **3.1.5 Treatment assignment/randomization**

Prior to patient signing of the informed consent form (ICF), the Investigators must contact the Sponsors in order to be informed that the respective cohort and stratum is open to enrollment. The assignment of a patient will be coordinated by the Sponsors in agreement with the Investigators.

### **3.1.6 Treatment blinding**

Not applicable. This is an open label study.

## **3.2 Rationale for the study design**

For a significant population of thrombocytopenic MF patients there are limited data about the safety of INC424 or what might be an appropriate dose. In all studies conducted to date with INC424, baseline PLT count of  $\geq 100 \times 10^9/L$  has been an inclusion criterion. However, thrombocytopenia is a frequent event in MF; as per epidemiology data (Mesa et al 2007), 16.5% of all MF patients are reported to have PLT counts  $< 100 \times 10^9/L$  at diagnosis, while in the intermediate risk-1, -2 or high-risk disease population the incidence of thrombocytopenia is estimated by medical experts to be higher. As noted in Section 1.2.4, thrombocytopenia was established as the DLT of INC424 in MF patients with a MTD of both 25 mg b.i.d. and 100 mg qd. In that study, some patients continued to receive INC424 while their platelet count ranged between 50 and  $100 \times 10^9/L$  (for details, see Section 3.4.5), but no patients with platelet counts below  $100 \times 10^9/L$  have initiated INC424 therapy, and therefore the MSSD for patients with low platelets needs to be directly established.

This clinical trial will be a single arm, safety and dose-finding phase Ib study. It will evaluate the safety of INC424 in the low-PLT MF population and will establish the MSSD. Gradually increasing doses of INC424, ranging from 5 mg b.i.d. to 15 mg b.i.d., will be used in the dose escalation part of the study. Initially, only patients with PLT counts  $75-99 \times 10^9/L$  (first stratum) will allow to be enrolled. Once safety in patients in the first stratum is established at the first two dose cohorts (5 mg b.i.d. and 5 mg q.AM / 10 mg q.PM) the eligible population will be further expanded to patients with PLT counts  $50-74 \times 10^9/L$  (second stratum).

Following determination of the MSSD, the safety expansion phase will be conducted. In the safety expansion phase, the safety and tolerability of the MSSD will be further evaluated, with the purpose of establishing that this dose is suitable for use in the low-platelet population of patients with MF. Moreover, estimates of efficacy will be obtained.

